5.3 Patient Exclusion Criteria

Patients will be ineligible for this study if they meet any one of the following criteria:

- The patient has an active malignancy and/or cancer history that may confound the
 assessment of the study endpoints. Patients with a past cancer history (within 2 years of
 entry) with substantial potential for recurrence and/or ongoing active malignancy must be
 discussed with the Sponsor before study entry. Patients with the following neoplastic
 diagnoses are eligible: non-melanoma skin cancer, carcinoma in situ (including
 superficial bladder cancer), cervical intraepithelial neoplasia, organ-confined prostate
 cancer with no evidence of progressive disease.
- Prior therapy with SL-401 or received any investigational drug within the prior 30 days or 5 half-lives of the investigational drug, whichever is longer.

^{*} An FCBP is a sexually mature female who: 1) has not undergone a hysterectomy or bilateral oophorectomy; or 2) has not been naturally postmenopausal for at least 24 consecutive months (i.e., has had menses at any time in the preceding 24 consecutive months).

- Prior anti-cancer therapy (chemotherapy, targeted agents, radiotherapy, and immunotherapy) within the prior 21 days, except for alkylating agents (e.g., melphalan) within the prior 28 days.
- 4. Prior treatment with POM.
- Primary refractory MM defined as disease that is non-responsive in patients that have never achieved at least stable disease or better with any therapy.
- 6. Any > grade 1 (according to the National Cancer Institute [NCI] Common Terminology Criteria for Adverse Events (CTCAE), v.4.03) adverse reaction unresolved from previous treatments or not readily managed and controlled with supportive care. The presence of alopecia of any and peripheral neuropathy ≤ grade 2 without pain is allowed.
- Previous allogeneic stem cell transplantation with active graft-versus-host-disease or treatment with immunosuppressive therapy in the 2 months prior to study entry.
- Daily requirement for corticosteroids >10 mg prednisone daily (or equivalent); inhaled corticosteroids are permitted.
- Patient is known to be human immunodeficiency virus positive, or have chronic or active hepatitis B (core- or surface antigen-positive) or active hepatitis C infection.
- 10. Clinically significant cardiovascular disease (e.g., uncontrolled or any New York Heart Association [NYHA] Class 3 or 4, congestive heart failure, uncontrolled or uncontrolled angina, history of myocardial infarction or stroke within 6 months prior to study entry, uncontrolled hypertension or clinically significant arrhythmias not controlled by medication).
- 11. Uncontrolled, clinically significant pulmonary disease (e.g., chronic obstructive pulmonary disease, pulmonary hypertension) that in the opinion of the Investigator would put the patient at significant risk for pulmonary complications during the study.
- Uncontrolled intercurrent illness including, but not limited to, uncontrolled infection, disseminated intravascular coagulation, or psychiatric illness/social situations that would limit compliance with study requirements.
- History of erythema multiforme or severe hypersensitivity to prior IMiDs such as thalidomide and lenalidomide.
- 14. The patient is receiving medications that are strong inhibitors of CYP1A2. Patients should have discontinued strong CYP1A2 inhibitors (e.g., ciprofloxacin and fluvoxamine [see Section 15.5]) at least 5 half-lives before beginning study drug.
- The patient continues to smoke cigarettes, which can induce CYP1A2.
- Inability to tolerate thromboprophylaxis (see section on concurrent medications).
- Pregnant or breastfeeding females.

5.4 Replacement of Patients

At the discretion of the Sponsor, additional patients may be enrolled to supplement patient data compromised due to premature study dropout or other reasons. During phase 1, patients who discontinue the study prior to completing the DLT evaluation period because of disease progression or for reasons unrelated to study therapy will be replaced. All patients in phase 2

and those treated at the MTD or recommended phase 2 dose as established in phase 1, who are not evaluable for response will be replaced.

6 Investigational Plan

6.1 Dose and Schedule Rationale

Under an Investigator-sponsored IND (#11314), the MTD of SL-401 as a daily \times 5 regimen in a phase 1/2 dose escalation study was determined to be 16.6 µg/kg/day. The principal DLTs consisted of hypoalbuminemia and edema (i.e., capillary leak syndrome), and the incidences of DLTs were 2 of 2 patients at the 22.12 µg/kg/day dose level, 1 of 8 patients at the 16.6 µg/kg/day dose level, and 1 of 18 patients at the 12.5 µg/kg/day dose level. The LFT and albumin results from the investigator-sponsored study investigating SL-401 indicate that most patients with clinically meaningful changes in these parameters following administration of SL-401 would be expected to recover to near baseline levels by 3-4 weeks following the initiation of therapy. These results therefore support administration of cycles every 28 days with the allowance to delay the start of a subsequent cycle to allow toxicity resolution. Furthermore, a single cycle of SL-401 demonstrated single agent activity in patients with relapsed or refractory AML or BPDCN, with the majority of major responses occurring at the 12.5 µg/kg/day dose level. Therefore, the risk/benefit profile of SL-401 appeared to be most favorable at the 12.5 µg/kg/day dose level, and this is the expected dose that will be used in future studies of SL-401. This is the highest dose level planned in combination with POM/DEX.

In the interest of optimizing patient safety in combination therapy, the dose escalation in phase 1 of the study will begin 2 dose levels below, or at 7 µg/kg/day, which was the lowest tested dose for this regimen (7.07 µg/kg/day) in the phase 1/2 study evaluating SL-401.

6.2 Overall Study Design

This is a phase 1/2 non-randomized, open-label, dose escalation, multicenter study. A cycle of therapy is 28 days. A Data Safety Review Committee (DSRC), which will include Sponsor representatives, Medical Monitor, biostatistician and study Investigators; will be established to review the accruing safety data and make safety decisions during the study, including dose escalation during phase 1. The DSRC will also periodically review data during phase 2 (at least 2 times per year, and more frequently in the event of DLTs, other severe or serious AEs or treatment—related deaths).

6.2.1 Phase 1: Dose Escalation

Run-In Cycle: SL-401 will be evaluated at doses of 7, 9, or 12 μg/kg/day, for 5 consecutive days (Days 1-5; with postponement as required by adverse events such that 5 doses over 10 days is permitted) as single agent during an initial Run-in Cycle. Upon completion of the Run-in Cycle patients will be evaluated for safety and response.

- Patients who do not experience a DLT during the Run-in Cycle will have POM/DEX added to their regimen at the assigned cohort dose.
- Patients who experience a DLT during the Run-in Cycle will be discontinued from study.

Table 7 details the SL-401/POM/DEX dose levels, beginning with dose level 1 to be evaluated.

Table 7: Dose Levels to be Evaluated

Dose Level	DLT EVALUTION PERIOD = RUN IN CYCLE and CYCLE 1				
	Run-In Cycle	Combination therapy Cycles 1 - 6			
	SL-401(IV) Daily on Days 1 – 5	SL-401(IV) Daily on Days 1 – 5	POM (oral) Daily on Days 1 – 21	DEX (oral) on Days 1, 8, 15 and 22	
-1	5 μg/kg	5 μg/kg	4 mg	40 mg	
1	7 μg/kg	7 μg/kg	4 mg	40 mg	
2	9 μg/kg	9 μg/kg	4 mg	40 mg	
3	12 μg/kg	12 μg/kg	4 mg	40 mg	

Cohorts of 3-6 patients will be treated at each dose level. All patients within a cohort must complete the Run-in Cycle and the first cycle of combination therapy (Cycle 1) before patients can be enrolled into the subsequent cohort of SL-401 (single agent) at the next higher dose. No intra-patient dose escalation is allowed. The first cohort of patients will receive SL-401 single agent at a dose of 7 µg/kg/day followed by SL-401 with POM/DEX. After all patients in this cohort complete the Cycle 1 of therapy, the dose for the second cohort of patients will increase to 9 µg/kg/day, conditional on the DLT rules described below. Similarly, after all patients in the second cohort complete Cycle 1 of therapy, the dose for the third cohort of patients will increase to 12 µg/kg/day, conditional on the DLT rules described below.

Beginning with the dose level 7 μg/kg/day of SL-401 in combination with POM/DEX, a decision to allow treatment at the next higher dose level will depend on the number of patients who experience a DLT during the Run-in cycle and first cycle of combination therapy (Cycle 1). If none of the initial 3 patients treated (0/3) experiences a DLT, then dose escalation will proceed and 3 new patients will be treated at the next higher dose of 9 μg/kg/day. If 1 of the initial 3 patients treated (1/3) experiences a DLT, the cohort will be expanded to include an additional 3 patients treated at the same dose 7 μg/kg/day. If only 1 patient (1/6) from this expanded cohort experiences a DLT, then 3 new patients will be treated at the next higher dose of 9 μg/kg/day. Expansion of the 9 μg/kg/day cohort to 6 patients, if necessary, will follow the same rules as the 7 μg/kg/day cohort. The same DLT rules will also apply to the 12 μg/kg/day cohort.

The highest dose intended for evaluation is 12 µg/kg/day in combination with POM/DEX. If this dose level is not declared the MTD after at least 6 patients are treated, it will be declared the maximum tested dose level and will be the dose recommended for phase 2 studies. Potential DLTs and laboratory abnormalities will be evaluated by the DSRC (comprised of the Principal and Co-principal Investigators, Sponsor's Medical Monitor, and biostatistician) on an ongoing basis, who will evaluate the safety/tolerability of each dose level prior to investigation of a

subsequent dose level. Although the dose escalation process is guided by the safety evaluation during the Run-in Cycle and Cycle 1 of treatment, cumulative toxicities observed in subsequent administrations should also be considered for the dose escalation decisions.

In the event that 2 patients within a cohort have a DLT, then the MTD will be exceeded and further dose escalation will not occur. The MTD is defined as the dose preceding the dose level at which 2 patients experience a DLT. The MTD will be used in phase 2 of the study. If the highest planned treatment dose is completed and determined to be safe and the MTD is not exceeded, the available PK and safety data will be reviewed to assess whether further dose escalation is justified. A patient who does not complete the first 2 cycles of treatment for reasons other than the occurrence of DLT will be replaced by another patient who will receive the same dose regimen if necessary to evaluate that cohort (e.g., if a patient is not evaluable for DLT but 2 others have experienced a DLT within the cohort, there will be no need to replace the patient as the MTD will have been exceeded).

In the event that a DLT occurs in 2 patients treated at the 7 µg/kg/day dose level, 5µg/kg/day may be considered by the DSRC as an alternative starting dose. In this event, a new cohort of 3 patients will receive 5 µg/kg/day including a single agent Run-in Cycle prior to the first cycle of combination therapy. The same DLT rules will apply to this dose level. If 2 or more patients experience a DLT at the 5 µg/kg/day dose level, the study will be halted.

SL-401 related toxicities are AEs that are considered by the Investigator to be either possibly, probably or definitely related to investigational SL-401. (Refer to Section 10.6 for more thorough guidance as to the assessment of "relatedness" in the context of investigational anticancer therapy). It should be noted that although the cycle length is 28 days, cycle duration may extend beyond 28 days in the setting of AEs, which are detailed in Section 7.7.2.

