 - Grade 3 nausea, vomiting or diarrhea lasting no longer than 48 hours (with resolution to Grade ≤ 1 or baseline) with optimal supportive care.
 - Grade 3 arthralgia, myalgia, fever, in the absence of neutropenia, lasting no longer than 48 hours (with resolution to grade ≤ 1 or baseline).
 - Grade 3 fatigue lasting < 7 days.
 - Grade 3 laboratory abnormalities that are asymptomatic and not considered clinically significant by the Investigator, that respond to or do not require intervention and resolve to ≤ grade 1 or baseline ≤ 28 days after the last infusion of SL-401.
- Grade 4 transaminase or creatine phosphokinase (CPK) elevation (confirmed within 24 hours of initial identification) regardless of duration or relationship to SL-401.

The period of evaluation for DLT will include the Run-in Cycle and Cycle 1 (the first cycle of combination therapy.

If none of the initial 3 patients treated (0/3) experiences a DLT, then dose escalation will proceed and 3 new patients will be treated at the next higher dose of 9 μg/kg/day. If 1 of the initial 3 patients treated

(1/3) experiences a DLT, the cohort will be expanded to include an additional 3 patients treated at the same dose 7 μ g/kg/day. If only 1 patient (1/6) from this expanded cohort experiences a DLT, then 3 new patients will be treated at the next higher dose of 9 μ g/kg/day. Expansion of the 9 μ g/kg/day cohort to 6 patients, if necessary, will follow the same rules as the 7 μ g/kg/day cohort. The same DLT rules will also apply to the 12 μ g/kg/day dose level.

The highest dose intended for evaluation is 12 µg/kg/day in combination with POM/DEX. If this dose level is not declared the MTD after at least 6 patients are treated, it will be declared the maximum tested dose level and will be the dose recommended for phase 2 studies. Potential DLTs and laboratory abnormalities will be evaluated by the data safety review committee (DSRC; comprised of the Principal and Co-principal Investigators, Sponsor's Medical Monitor, and biostatistician) on an ongoing basis, who will evaluate the safety/tolerability of each dose level prior to investigation of a subsequent dose level. Although the dose escalation process is guided by the safety evaluation during the Run-in Cycle and the first combination cycle (Cycle 1) of treatment, cumulative toxicities observed in subsequent administrations should also be considered for the dose escalation decisions and recommended phase 2 dose

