In the event that 2 patients within a cohort have a DLT, then the MTD will be exceeded and further dose escalation will not occur.

The MTD of the combination therapy is defined as the dose preceding the dose level at which 2 patients experience a DLT during the Run-in Cycle and Cycle 1 of combination therapy. The MTD of the combination will be used in phase 2 of the study. If the highest planned treatment dose is completed and determined to be safe and the MTD is not exceeded, the available PK and safety data will be reviewed to assess whether further dose escalation is justified. A patient who does not complete the first cycle of treatment for reasons other than the occurrence of DLT will be replaced by another patient who will receive the same dose regimen if necessary to evaluate that cohort (e.g., if a patient is not evaluable for DLT but 2 others have experienced a DLT within the cohort, there will be no need to replace the patient as the MTD will have been exceeded).

In the event that a DLT occurs in 2 patients treated at the 7 μ g/kg/day dose level, 5 μ g/kg/day will be considered by the DSRC as an alternative starting dose. In this event, a new cohort of 3 patients will receive 5μ g/kg/day for the first cycle. The same DLT rules will apply to this dose level. If 2 or more patients experience a DLT at the 5 μ g/kg/day dose level, the study will be halted.

Phase 2

During phase 2, at least 14 additional patients (total, 20 patients) will be treated at the MTD or maximum tested dose at which multiple DLTs are not observed (identified in phase 1). During phase 2, the initial Run-in Cycle (SL-401 single agent) will no longer be administered. However, the first 6 patients treated at the MTD without the run in cycle will also be assessed for DLT during the first cycle of therapy. In the event that more than 1 DLT is identified in these initial 6 patients during phase 2, consideration will be given to the administration of a reduced SL-401 dose in the remainder of phase 2, or re-institution of the SL-401 single agent Run-in Cycle for the remainder of phase 2.

Dose Modification:

Patients will be evaluated for AEs at each visit with the NCI CTCAE, v.4.03, used as a guide for the grading of severity.

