6.2.3 Maximum Tolerated Dose Definition

The MTD is defined as the dose preceding the dose level at which 2 patients experience a DLT during treatment in the Run-in Cycle and Cycle 1. A total of at least 6 patients must be evaluated in order to confirm the MTD. The MTD will be used in phase 2 of the study. If the highest planned treatment dose is completed and determined to be safe and the MTD is not exceeded, the available PK and safety data will be reviewed to assess whether further dose escalation is justified.

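### The top-dose rule in Section 6.2.1 names 12 µg/kg/day for phase 2 even after two or more DLTs among six patients, where the MTD definition names 9 µg/kg/day

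*Protocol*

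**What the plan says.** The planned levels are 7, 9 and 12 µg/kg/day, with 5 as a fallback (synopsis Table 1; Section 6.2.1, Table 7). The 3+3 rules hold at the top level too: "The same DLT rules will also apply to the 12" µg/kg/day cohort (Section 6.2.1).

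The sentence at issue follows directly. If the 12 µg/kg/day "dose level is not declared the MTD after at least 6 patients are treated, it will be declared the maximum tested dose level", and that level is the dose recommended for phase 2. The synopsis (DLT Assessment) has the same condition: "is not declared the MTD after at least 6 patients are treated, it will be declared the maximum tested dose level".

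The MTD is defined elsewhere:

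- Synopsis: "The MTD of the combination therapy is defined as the dose preceding the dose level at which 2 patients experience a DLT".
- Section 6.2.1: "In the event that 2 patients within a cohort have a DLT, then the MTD will be exceeded and further dose escalation will not occur". Phase 2 then uses the MTD.
- Section 6.2.3: "The MTD is defined as the dose preceding the dose level at which 2 patients experience a DLT during treatment", and "A total of at least 6 patients must be evaluated in order to confirm the MTD".

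Escalation beyond 12 may be considered only under a different condition: "If the highest planned treatment dose is completed and determined to be safe and the MTD is not exceeded" (Section 6.2.1, with the same condition in the synopsis and Section 6.2.3).

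**The concern.** The sentence should separate a top dose that was tolerated from one that was not. Its test is whether 12 was declared the MTD. By the protocol's definition, a dose becomes the MTD only when the level above it produces two DLT patients, and nothing above 12 is planned. So the test gives the same answer whatever the DLT count at 12, and with two or more DLTs among six it sends to phase 2 a dose that the next paragraph says has exceeded the MTD.

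Finding the MTD or maximum tested dose is a primary objective (Section 4.1), and this sentence sets the dose for at least 14 further patients (Section 6.2.4).

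**Working it through.** The protocol gives no figure to reproduce here. The check is of decision logic, followed by a calculation of how often the conflicting branch would be reached.

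**Step 1: outcomes at 12 µg/kg/day**

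| Outcome at 12 | Top-dose sentence, read literally | MTD definition | Agreement |
|---|---|---|---|
| 2/3 or 3/3, cohort closed at 3 | does not apply (fewer than 6 treated) | MTD is 9 | no conflict |
| 0/6 or 1/6 | 12 | MTD not exceeded | no conflict |
| 1/3, then 1, 2 or 3 of the next 3 (2/6 to 4/6) | 12 | MTD is 9 | conflict |
| 0/3, then 2 or 3 of the next 3 (2/6 or 3/6) | 12 | MTD is 9 | conflict |

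The third row arises from the ordinary expansion after 1/3. The fourth arises because the sentence itself requires at least 6 patients before 12 is declared the maximum tested dose, so a 0/3 cohort also has to be filled.

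**Step 2: whether further escalation resolves it**

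It does not. Going above 12 is open only if 12 is judged safe and the MTD is not exceeded. Two DLTs close that route, so no higher level can make 12 the MTD in the conflicting rows.

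**Step 3: how often the branch is reached, given that the 12 level is opened**

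Assumptions, not taken from the protocol: a true DLT rate p, and independence between patients. Let f_k be the Binomial(3, p) probability of k DLTs.

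- Closes at 3: f2 + f3
- Ends at 0 or 1 of 6: f0(f0 + f1) + f1·f0
- Conflict, cohort filled to 6: f0(f2 + f3) + f1(1 − f0)
- Conflict, one-at-a-time enrolment stopped at the second DLT (which must fall on patient 6): 5p²(1 − p)⁴

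At p = 0.20: f0 = 0.512, f1 = 0.384, f2 + f3 = 0.104. Conflict, filled to 6: 0.512 × 0.104 + 0.384 × 0.488 = 0.053 + 0.187 = 0.241 (from unrounded terms). Conflict, one at a time: 5 × 0.04 × 0.4096 = 0.082.

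| Assumed p | Closes at 3 | 0 or 1 of 6 | Conflict, filled to 6 | Conflict, one at a time |
|---|---|---|---|---|
| 0.10 | 0.028 | 0.886 | 0.086 | 0.033 |
| 0.20 | 0.104 | 0.655 | 0.241 | 0.082 |
| 0.30 | 0.216 | 0.420 | 0.364 | 0.108 |
| 0.40 | 0.352 | 0.233 | 0.415 | 0.104 |

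The first three result columns sum to 1 in each row, up to rounding. The filled-to-6 figure is an upper bound, because accrual might stop once a second DLT is seen.

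**Step 4: low end from the earlier single-agent study**

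At 12.5 µg/kg/day daily × 5, the protocol reports 1 DLT in 24 patients (Table 5) or 1 in 18 (Section 6.1).

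- p = 1/24 = 0.042: f0 = 0.880, f1 = 0.115, f2 + f3 = 0.0051. Conflict: 0.880 × 0.0051 + 0.115 × 0.120 = 0.018.
- p = 1/18 = 0.056: f0 = 0.842, f1 = 0.149, f2 + f3 = 0.0089. Conflict: 0.842 × 0.0089 + 0.149 × 0.158 = 0.031.

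**The case against.** The strongest reply is that the conflict appears only when one sentence is isolated. The sentence before it applies the usual DLT rules at 12. The next paragraph says two DLTs exceed the MTD and that the MTD goes into phase 2. Section 6.2.4, the synopsis and Section 11.3 limit the maximum tested dose to one without multiple DLTs, which rules out 12 in this branch. The Data Safety Review Committee decides on doses, and the first 6 phase 2 patients are checked for DLTs again. On this view it is an editorial slip. The 10 to 40% DLT rates also sit well above the 4 to 6% already seen near this dose.

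Much of this stands. The intended answer is clearly 9, the literal reading is unlikely to be followed, and the earlier data belong in the range as its low end. Those data are from a single agent, one cycle and other diseases, so the rate with pomalidomide and dexamethasone over two cycles could be higher.

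Two things do not follow. Clear intent elsewhere does not correct the sentence, and the qualifier about multiple DLTs is not used consistently: Sections 5.1 and 6.3, for example, give the MTD or maximum tested dose without it. The phase 2 check comes after patients have been exposed, and more than one DLT there leads only to consideration of a lower dose or a return to the run-in cycle.

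**Conclusion.** The concern holds. The top-dose sentence uses a condition that cannot fail once six patients are treated at 12 µg/kg/day. With two or more DLTs among them it contradicts the MTD definition: 12 against 9. The error is confined to that sentence, in Section 6.2.1 and the synopsis.

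The branch is reachable under the protocol's own 3+3 rules. Its probability, once the 12 level is opened, runs from about 2 to 3% at the earlier single-agent DLT rates to 41% at an assumed 40% rate with the cohort filled to six. With one-at-a-time enrolment stopped at the second DLT, it is 3 to 11% across assumed rates of 10 to 40%. These figures rest on the assumed rates and on independence between patients. They describe how often the two rules would disagree, not how often a wrong dose would be given.

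Severity is modest. It should still be corrected, because it is an operative dose-selection rule tied to a primary objective.

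**What to change.** In Section 6.2.1 and in the synopsis (DLT Assessment), replace the condition that 12 was not declared the MTD with the DLT count: *if 0 or 1 of at least 6 DLT-evaluable patients at this level has a DLT (MTD not exceeded)*.

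Add: *If 2 or more patients at this level have a DLT, the MTD is the preceding dose (9 µg/kg/day), confirmed in at least 6 patients per Section 6.2.3, and that dose is used in phase 2.* The added sentence restates the existing definition, but it puts both outcomes in one place.

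With this wording every row of the outcome table gives one dose. The cost is one sentence replaced and one added, in two places, by amendment. No visits or analyses are added, and any extra patients needed to reach six at 9 µg/kg/day are already required by Section 6.2.3.
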